9.2.1.3 Accrual

We anticipate enrollment of approximately 1-2 patients per month to the protocol with accrual completed in approximately 3-4 years.

9.2.1.4 Stratification Factors

There will be no stratification factors upon initial enrollment in the protocol.

9.3 Statistical Methods of Analysis

9.3.1 **Safety/Toxicity:** NCI CTC version 4.0 will be used for scoring the toxicity and adverse events. The severity and frequency of the toxicity will be tabulated by the tested dose or doses using descriptive statistics. The proportions of patient who experienced grade 3 or above toxicities will be estimated, along with 95%

confidence intervals by each type of toxicity.

9.3.2 Pseudo-progression: The proportion of patients who had pseudo-progression will be reported with 95% confidence intervals.

9.3.2 PFS-6: The definition of progression will be based on RANO criteria (19). Progression free will be measured from initial salvage starting date to the date of progressive disease is defined (documented). The proportion of PFS-6 will be estimated along with 95% confidence intervals using the exact binomial method.

9.3.3 OS: the survival time is defined from the date of treatment start to the date of death. Patients who have not died by the analysis data cut-off date will be censored at their last date known to be alive. The Kaplan-Meier method will be used to estimate one year survival, and median survival along with 80% confidence intervals.

9.3.4 Radiation Toxicity: descriptive statistics will be used to summarize radiation toxicity based on the RTOG/EORTC acute and late radiation morbidity scoring criteria (see appendix B and C) for all patients who had any radiation treatment in this study.

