5.5 Criteria for Removal from Study

Patients will be removed from study when any of the criteria listed in Section 5.3 applies. The reason for study removal and the date the patient was removed must be documented in the Case Report Form. Patients will continue to be followed for overall survival. Data from medical oncology, including MRI reports and additional chemotherapy, will be collected until time of death.

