7. STUDY CALENDAR

See Appendix D. Baseline evaluations and imaging are to be conducted within 4 weeks prior to start of protocol therapy. Every effort should be made to adhere to the protocol timeline as closely as possible, but if studies are delayed or missed as a result of unavoidable conflicts such as hospitalization at an outside facility, deteriorating of patient status, or other adversity precluding presentation for evaluation, it will not be considered a protocol deviation. Toxicity assessments that cannot be done in person will be completed over the phone.

In order to minimize the need for research-only in-person visits, telemedicine visits may be substituted for in person clinical trial visits or portions of clinical trial visits where determined to be appropriate and where determined by the investigator not to increase the participants risks. Prior to initiating telemedicine for study visits the study team will explain to the participant, what a telemedicine visit entails and confirm that the study participant is in agreement and able to proceed with this method. Telemedicine acknowledgement will be obtained in accordance with the Guidance for Use of Telemedicine in Research. In the event telemedicine is not deemed feasible, the study visit will proceed as an in-person visit. Telemedicine visits will be conducted using HIPAA compliant method approved by the Health System and within licensing restrictions.

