8. MEASUREMENT OF EFFECT

Patients with measurable disease will be assessed by standard criteria. For the purposes of this study, patients should be re-evaluated approximately every 8 weeks.

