8.1 Antitumor Effect

Response and progression will be evaluated in this study using the international criteria proposed by the Response Assessment in Neuro-Oncology Working Group (RANO) (19).

8.1.1 **Definitions**

Evaluable for toxicity. All patients will be evaluable for toxicity from the time of their first treatment with LDFRT.

Evaluable for objective response. Only those patients who have received at least one cycle of therapy, and have had their disease re-evaluated will be considered evaluable for response. These patients will have their response classified according to the definitions stated below. (Note: Patients who exhibit objective disease progression prior to the end of cycle 1 will also be considered evaluable.)

8.1.2

8.1.3 **Methods for Evaluation of Disease**

All baseline evaluations should be performed as closely as possible to the beginning of treatment and never more than 4 weeks before the beginning of the treatment.

The same method of assessment and the same technique should be used to evaluate patients at baseline and during follow-up. Imaging-based evaluation is preferred to evaluation by clinical examination when both methods have been used to assess the antitumor effect of a treatment.

MRI: T1 with gadolinium, T2 and FLAIR sequence MRI techniques should be performed with cuts of 5 mm or less in slice thickness contiguously.

Corticosteroid use: Dosages of corticosteroids will be recorded at baseline as well as follow-up visits and will be incorporated into the response criteria.

Clinical examination: Neurologic deficits and symptoms will be recorded at baseline as well as follow-up visits and will be incorporated into the response criteria.

8.1.4 **Progression-Free Survival**

Progression free survival will be measured from the date of initiation of salvage treatment to the date of documented progressive disease according to the RANO criteria (19).

8.1.5 **Overall Survival (OS)**

OS is defined as the duration of time from start of treatment to time of death from any cause.

8.1.6 **Pseudo-progression**

September 29, 2022

Pseudo-progression will be defined and MRI changes including T1 post-gadolinium, T2 or T2 variants such as FLAIR imaging, with or without clinical deterioration and/or increase in dexamethasone dose which stabilizes or reverses on later evaluations without a change in oncologic intervention.

8.1.7 **Toxicity**

Toxicity will be monitored according to the criteria outlined in section 5.2.1.

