APPENDIX D: STUDY CALENDAR

Cycles 1 – 6: Radiation and Temodar

	Pre-Study ¹	Wk 1	Wk 2	Wk 3	Wk 4	Wk 5	Wk 6	Wk 7	Wk 8	Wk 9	Wk 10	Wk 11	Wk 12	Wk 13	Wk 14	Wk 15	Wk 16	Wk 17	Wk 18	Wk 19	Wk 20	Wk 21	Wk 22	Wk 23	Wk 24	
LDFRT²		X				X				X				X				X					X			
Temozolomide		X				X				X				X				X					X			
Informed consent	X																									
Demographics	X																									
Medical history³	X	X				X				X				X				X					X			
Physical exam	X																									
Vital signs	X																									
Height	X																									
Weight	X																									
Performance status	X	X				X				X				X				X					X			
CBC with diff⁴	X	X	X	X	X	X	X	X	X	X	X	X	X	X	X	X	X	X	X	X	X	X	X	X	X	
CMP⁴	X	X	X	X	X	X	X	X	X	X	X	X	X	X	X	X	X	X	X	X	X	X	X	X	X	
NCI Common Toxicity Criteria	X	X				X				X				X				X					X			
RTOG Acute/Late Morbidity Criteria⁵	X	X				X				X				X				X					X			
MRI⁶	X								X									X								X
B-HCG	X																									

¹ Baseline evaluations and imaging are to be conducted within 4 weeks prior to start of protocol therapy.² Patients receive temozolomide (150 to 200 mg per square meter) and 0.5 Gy of radiation therapy twice daily (at least 6 hrs. apart) for 5 days during each 28 day cycle for a total of 6 cycles or until the time of disease progression. Cycles 1 through 6 will always start on a Monday.³ Medical history should be a complete history at pre-study evaluation, but later histories may be interval toxicity evaluations only.

⁴Laboratory tests will be requested and performed at the discretion of the patient's medical oncologist.

⁵Use RTOG Acute Toxicity Criteria during RT and for first 6 months following completion of RT. Use RTOG Late Toxicity Criteria at baseline and at scheduled intervals 6 months following completion of RT.

⁶MRI imaging will be performed approximately every 2 months during temozolamide and then according to the schedule outlined above. MRI sequences must include at a minimum T1 with gadolinium, T2 and FLAIR sequences. Other sequences may be obtained at the provider's discretion. An MRI which is delayed or missed as a result of the deterioration of the patient's clinical condition or other adversity will not be considered a protocol violation.

Cycles 7 – 12: Temozolide Only and Follow up

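### PFS-6 is a plain binomial proportion that names neither death nor unknown status at month 6, which leaves it open to upward bias from informative missingness

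*Combined protocol and SAP*

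**What the plan says.** PFS-6 is the first phase II secondary objective (1.2.2.1). Its analysis is in the second of the two paragraphs numbered 9.3.2: "The proportion of PFS-6 will be estimated along with 95% confidence intervals using the exact binomial method". Section 8.1.4 runs progression-free survival from the start of salvage treatment "to the date of documented progressive disease according to the RANO criteria (19". The endpoint text in 9.1.2 and the analysis text in 9.3 have the same end point. None of the three names death.

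On assessment, section 8 says that "patients should be re-evaluated approximately every 8 weeks". The Appendix D calendar marks MRIs at about weeks 8, 16 and 24 in the first six cycles, and the next at about week 32. No window is tied to month 6.

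On missing scans, Appendix D says that an MRI "delayed or missed as a result of the deterioration of the patient's clinical condition or other adversity will not be considered a protocol violation". Section 7 says the same of study procedures in general, citing "deteriorating of patient status, or other adversity precluding presentation for evaluation, it will not be considered a protocol deviation".

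For patients removed under 5.5, survival follow-up continues and "Data from medical oncology, including MRI reports and additional chemotherapy, will be collected until time of death".

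OS is handled differently. Section 8.1.5 counts death from any cause, and 9.3.3 gives a censoring rule and Kaplan-Meier estimation. PFS-6 has neither.

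**The concern.** An exact binomial proportion is valid only if each patient in the denominator can be classed as a success or a failure. Here the failure is a documented event, so a patient with no documentation has no failure. The plan does not say whether that patient is then a success, a failure or left out.

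The gap matters because the missing data are not random. Both excusal clauses name deterioration as a reason for a missed assessment, and a deteriorating patient is more likely than others to have progressed. A patient who declines, misses the scan and dies before month 6 has no progression-free survival event as the text stands. At stake is an estimate that could be carried into later planning: the February 2017 amendment (2.3) intends the OS result to serve as a possible reference for a future trial, and PFS-6 would be reported beside it.

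**Working it through.** The plan states no target, power or expected value for PFS-6, so there is no figure to reproduce. The 31 patients were sized on response rate (9.2.1.2).

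**Step 1. One patient followed through the text.** Suppose a patient is stable at week 16, deteriorates, misses the week-24 MRI and dies in month 5 with no progression recorded.
- Under 8.1.5 this is an OS event.
- Under 8.1.4, 9.1.2 and 9.3 there is no documented progression, so there is no progression-free survival event.
- Under section 7 and Appendix D the missed scan is not a deviation.
- Under 9.3 no rule says how to classify the patient.

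Such early deaths are not remote. Assuming exponential survival with the interim median OS of 9.5 months, 1 − 0.5^(6/9.5) = 1 − 0.646, so roughly one patient in three dies by month 6. The documents do not say how many of these would lack a documented progression date.

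**Step 2. What the unstated rule is worth.** Inputs are n = 31 (9.2.1.2) and the interim median PFS of 4.0 months (2.3). Assuming exponential PFS, the proportion free at month 6 is 0.5^(6/4.0) = 0.354, and 31 × 0.354 = 10.96. So take x = 11 known progression-free and let m patients have unknown status (m is assumed). The three possible rules give x/n, x/(n − m) and (x + m)/n, with exact 95% intervals:

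| m | Unknown = failure | Unknown excluded | Unknown = success |
|---|---|---|---|
| 3 | 11/31 = 35.5% (19.2–54.6) | 11/28 = 39.3% (21.5–59.4) | 14/31 = 45.2% (27.3–64.0) |
| 6 | 11/31 = 35.5% (19.2–54.6) | 11/25 = 44.0% (24.4–65.1) | 17/31 = 54.8% (36.0–72.7) |

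The spread is 45.2 − 35.5 = 9.7 points for three patients and 54.8 − 35.5 = 19.3 points for six. Each patient moved from failure to success adds 1/31 = 3.2 points.

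**Step 3. Scan timing.** Week 24 is day 24 × 7 = 168. Month 6 is day 6 × 30.4375 = 182.6. The gap is 14.6 days, and the next scan is at about day 32 × 7 = 224. Under the same exponential assumption, with every scan on time, recorded PFS-6 reflects status at week 24 (5.52 months): 0.5^(5.52/4.0) = 0.384, which is 3.1 points above 0.354 before rounding. If a share f of week-24 scans falls after month 6, those patients were last seen at week 16 (3.68 months), where the value is 0.529. Recorded PFS-6 is then (1 − f) × 0.384 + f × 0.529, which is 0.399, 0.413 or 0.428 for f = 10%, 20% or 30%. The documents give no value for f.

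**The case against.** The strongest reply is that the direction of error depends on a rule the plan does not state. If unassessed patients were counted as failures, the error would be downward. Excusing a late scan is a compliance matter and does not classify the patient in the analysis. Section 8.1.3 brings neurologic status and steroid dose into the response criteria, so a missed MRI need not hide progression. Most of the first 22 patients had treatment-related MRI worsening (2.3), and reading that as progression would lower PFS-6. All of this stands, and it is why the text supports openness to upward bias and not a known net bias. It does not supply the missing rule.

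The timing figures are also soft. The 4.0-month median is itself an observed value, so adding scan delay to it partly counts the delay twice, and the late-scan shares are assumed. An excess of about 3 points with punctual scans is ordinary for scan-based assessment and small beside a 95% interval about 35 points wide.

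A reader might infer three stronger things that the documents do not support:
- That no scan is scheduled near month 6. The calendar has one at about week 24; only a window is missing.
- That scanning stops after removal. Section 5.5 keeps collecting MRI reports, and the last Appendix D footnote continues MRI until death, at the provider's discretion only from 12 months after temozolomide ends. What is missing is a stated interval and RANO reading for removed patients.
- That every error raises PFS-6. Pseudo-progression is a documented counter-example.

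**Conclusion.** The gap is real and should be closed before the analysis. As written, PFS-6 has documented progression as its only event, omits death, has no month-6 window and has no rule for unknown status, while the patients most likely to be unassessed are those in decline. Counting them as progression-free or dropping them would both raise the estimate relative to treating them as failures.

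The size is conditional: about 10 points between the extreme rules if three of 31 patients are unknown, and about 19 points if six are. These figures rest on an assumed 11 known progression-free patients and assumed values of m. The true number of unknown patients, and the offsetting effect of pseudo-progression, cannot be obtained from the documents. PFS-6 carries no hypothesis or decision threshold, and the promise criterion on one-year OS in 9.2.1.2 is unaffected.

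**What to change.** In the PFS-6 paragraph of 9.3, with matching wording in 8.1.4 and 9.1.2:

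1. Keep all treated patients in the denominator.
2. Count as an event RANO progression documented by month 6, or death from any cause by month 6.
3. Count as progression-free at 6 months only a patient who is alive at month 6 and has an evaluable assessment at or after about week 24 showing no RANO progression.
4. Count every patient without such an assessment as a failure, including those whose scan was missed through deterioration.
5. Report how many patients were failures under item 4 alone.
6. Add a Kaplan-Meier estimate of six-month PFS, with death as an event, as a sensitivity analysis. It should not replace the main rule, because censoring deteriorating patients would itself be informative.

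The cost is protocol and SAP wording. No extra scans are needed, and the rule can be applied to the 22 patients already treated by February 2017 as well as to later ones. The downside is a slightly lower, conservative PFS-6. A patient who misses a scan for reasons unrelated to disease is a failure. So is one who is clean at week 16 and first shows progression at a late scan after month 6. The count in item 5 and the estimate in item 6 let the reader see how much this matters.

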10. ADVERSE EVENTS AND RECORDING

10.1 Definition of Adverse Event (AE)

An adverse event is the development of an undesirable medical condition or the deterioration of a pre-existing medical condition during or following an exposure to a treatment, whether or not considered causally related to the treatment. An undesirable medical condition may be symptoms (headache, nausea), signs (tachycardia, enlarged liver), or abnormal results of an investigation (MRI, laboratory finding). In clinical trials, from the time of signing an informed consent, an AE may include an undesirable medical condition, occurring at any time, even if no trial treatment has been administered.

10.2 Radiation Related Adverse Events

All radiation related adverse events will be recorded on the local toxicity case report forms.

10.3 Chemotherapy Related Adverse Events

The adverse events (both hematologic and non-hematologic) that patients experience due to chemotherapy will be recorded on appropriate case report forms only if they are greater than or equal to grade 3, result in a delay in treatment, or are required to be reported per institutional guidelines.

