1.2.2 Phase II Secondary Objectives

1.2.2.1 To estimate the 6 month progression free survival in patients treated with LDFRT plus temozolomide for recurrent HGG.

1.2.2.2 To estimate the rate of pseudoprogression in patients treated with LDFRT plus temozolomide for recurrent HGG

1.2.2.3 To characterize the chronologic sequence of pseudoprogression in patients treated with LDFRT plus temozolomide for recurrent HGG.

1.2.2.4 To estimate the hematologic toxicity of salvage LDFRT + temozolomide.

1.2.2.5 To estimate the radiation-associated acute and long term neurologic toxicity of salvage LDFRT + temozolomide.

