SAE event in 9 out of 35 patients. $\Pr(\text{Risk}>0.2 \mid \text{Data}) = 0.64$
SAE event in 10 out of 40 patients. $\Pr(\text{Risk}>0.2 \mid \text{Data}) = 0.63$
SAE event in 11 out of 45 patients. $\Pr(\text{Risk}>0.2 \mid \text{Data}) = 0.62$
SAE event in 13 out of 55 patients. $\Pr(\text{Risk}>0.2 \mid \text{Data}) = 0.61$

Operating characteristics:

Underline true SAE rate	Probability declare unsafe	Average sample size
0.10	3.3	160
0.15	18.4	140
0.20	60.5	91
0.30	99.7	24
0.35	100	17

All SAEs or toxicity events will be tabulated by type and grade based on NCI CTC Version 4.0 for toxicity and adverse events. SAEs with an attribution of possible or above will be evaluated for early stopping. Proportion of individual type of SAE event will be estimated using the binomial distribution along with 95% confidence interval (exact method).

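### Whether a grade 1-2 adverse event reaches the case report form depends on which treatment it is attributed to, which conflicts with tables that report the combination's toxicity by grade with no lower limit

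*Combined protocol and SAP*

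**What the plan says.** Section 10.1 defines an adverse event "whether or not considered causally related to the treatment". The next two sections then set recording rules by cause:

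- Section 10.2: "All radiation related adverse events will be recorded on the local toxicity case report forms".
- Section 10.3: events due to chemotherapy, hematologic or not, "will be recorded on appropriate case report forms only if they are greater than or equal to grade 3, result in a delay in treatment". A third trigger completes that sentence: "or are required to be reported per institutional guidelines".

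The reporting side has no such filter. The safety monitoring text in section 9.2.1.2 states: "All SAEs or toxicity events will be tabulated by type and grade based on NCI CTC Version 4.0 for toxicity and adverse events". Section 9.3.1 states: "The severity and frequency of the toxicity will be tabulated by the tested dose or doses using descriptive statistics". It adds 95% confidence intervals only for grade 3 or above proportions. The Phase II secondary endpoints in section 9.1.2.1 ask for treatment-associated NCI toxicity of the combination for each patient, again with no grade limit. Section 1.2.2.4 sets the objective "To estimate the hematologic toxicity of salvage LDFRT + temozolomide".

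**The concern.** The trial studies a combination, and its toxicity tables are meant to describe that combination. A rule that keeps mild events attributed to one component and drops those attributed to the other makes the tables depend on a judgement that is hard to make here. Under cohort 1, the schedule that section 2.3 says all patients follow, radiation is given on the five temozolomide days of each of the first six cycles. Fatigue, alopecia, headache and seizures (convulsions) are listed as risks of both treatments in sections 5.1 and 5.2.4. Section 2.2 presents the radiation as a chemo-potentiator, so added toxicity could well look like temozolomide toxicity, the category that section 10.3 thins out.

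At stake is the completeness of the descriptive grade 1-2 tables, including the hematologic ones. A reader of those tables could take unrecorded mild events as events that did not occur.

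**Working it through.** The documents give no adverse event rate or attribution split, so there is no stated figure to reproduce. The check sets the recording rules against the reporting commitments.

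**Step 1. What section 10 requires for one non-serious grade 1-2 event, such as a headache:**

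| Attributed to | Required on the form? |
|---|---|
| Radiation | Yes (10.2) |
| Temozolomide, no delay, not institutionally reportable | No (10.3) |
| Both | Unclear: 10.2 would keep it, 10.3 would not, and neither takes precedence |
| Tumour, or neither treatment | No rule, although 10.1 counts it as an adverse event |

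**Step 2. What the tables need.** Sections 9.1.2.1, 9.2.1.2 and 9.3.1 need the first three rows in full. The fourth row matters less for them, because section 9.1.2.1 limits the toxicity endpoint to treatment-associated events. The missing rule there conflicts mainly with the definition in section 10.1.

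**Step 3. Illustration of size.** Inputs: N = 31 (section 9.2.1.2). Three values are assumed: p, the true share of patients with a given grade 1-2 event; f, the fraction of those attributed to chemotherapy alone; and d, the fraction of the latter that delays treatment. It is also assumed that every other event is recorded and that none is institutionally reportable.

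Recorded = N × p × (1 − f × (1 − d)).

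With p = 0.60, the expected number is 31 × 0.60 = 18.6. Taking d = 0 and then d = 0.20:

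- f = 0.25: 18.6 × 0.75 = 13.95, and 18.6 × 0.80 = 14.88.
- f = 0.50: 18.6 × 0.50 = 9.3, and 18.6 × 0.60 = 11.16.
- f = 0.75: 18.6 × 0.25 = 4.65, and 18.6 × 0.40 = 7.44.

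With p = 0.30, the expected number is 9.3, and f = 0.50 gives 4.65 to 5.58. The recorded share does not depend on p. It runs from 25% to 80% over these values of f and d.

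**Step 4. What the floor leaves intact.** Dose-limiting toxicity (5.2.1, 9.1.2.1.1) and the proportions with intervals in 9.3.1 use grade 3 or above, which section 10.3 records. One-year overall survival does not use these data.

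One small gap remains above the floor. Section 9.1.2.1.1 defines dose-limiting toxicity without an attribution condition, while sections 5.2 and 5.2.1 require at least possible attribution. A non-serious grade 3 cytopenia attributed to neither treatment would count under the first definition but has no recording rule in section 10.

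**The case against.** The strongest reply is that section 10 is not the only route by which events are captured:

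- Section 8.1.3 has neurologic deficits and symptoms recorded at baseline and follow-up visits, with no attribution condition.
- Appendix D schedules NCI and RTOG scoring each cycle. Appendix B grades CNS findings, white cells, platelets, neutrophils and hematocrit, including grades 1 and 2.
- Section 11.2 sends serious events to the IRB whatever their cause, subject to its timing rules for deaths.
- Section 9.1.2.1 itself asks for NCI toxicity per patient, so section 10.3 might be read as the exception. The forms themselves are not in the documents.
- A grade 3 floor for a drug described as standard treatment is a defensible choice.

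Much of this stands, and it rules out three stronger readings that a reader might infer:

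1. **That tumour-attributed events are not captured.** Nothing excludes them. They lack a form rule when non-serious.
2. **That neurologic toxicity is biased downwards because no earlier record would exist to regrade.** The visit record and the RTOG scores would exist.
3. **That the hematologic table would show almost no grade 1-2 events, or that most patients are affected.** The first needs nearly every cytopenia to be attributed to temozolomide alone. The second takes the imaging changes in section 2.3 as evidence about adverse event attribution. The documents support neither.

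The reply does not remove the conflict. RTOG grades are on a different scale from the planned NCI tables, and Appendix B has no lymphocyte row, although lymphopenia is a listed temozolomide risk and section 2.3 reports a lymphocytopenia SAE attributed to treatment. The section 8.1.3 record serves response assessment and asks for no toxicity grade. Scheduling an NCI assessment does not put its result on the form when section 10.3 says it need not go there.

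**Conclusion.** The point holds in a limited form. Followed as written, sections 10.2 and 10.3 give incomplete grade 1-2 counts in the NCI CTC tables of 9.2.1.2 and 9.3.1. The shortfall falls on chemotherapy-attributed events that cause no delay and are not institutionally reportable. Events attributed to both treatments are left unresolved.

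The size cannot be fixed from the documents. The 25% to 80% range rests wholly on assumed attribution and delay fractions and is not an estimate for this trial. The consequence is confined to descriptive safety reporting and the hematologic toxicity objective. It is worth correcting because the repair is cheap and uses assessments that are already scheduled, but it does not bear on the trial's main conclusion.

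**What to change.** Replace sections 10.2 and 10.3 with one rule that does not depend on attribution: record every grade 3 or above event and every neurologic event of any grade. The existing triggers for treatment delay and institutional reporting can stay. Make attribution a separate field that allows both, tumour or neither, and that can be revised later.

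Take hematologic grades directly from whatever blood counts are obtained. State that these counts are at the oncologist's discretion (section 5.1.1 and Appendix D, footnote 4), so the grades may be incomplete.

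Wherever a grade 3 floor is kept for a class of event, and for data already collected under section 10.3, restrict or label the 9.2.1.2 and 9.3.1 tables so that unrecorded grade 1-2 events are not read as absent.

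The cost is rewording and modest extra form entry, with no new visit or test. One trade-off should be stated: a common floor for other events would drop some mild radiation-related events that section 10.2 now keeps, unless the sponsor records all grades for those classes whatever the attribution.
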